**b. Vulnerable Populations**

- Pregnant women will be included, as this is the primary study population. The pregnant women randomized in this study are already prescribed magnesium sulfate for preeclampsia and the dosing regimens proposed are doses that are already administered at hospitals in the United States, with every hospital utilizing its own specific dosing protocol.
- Neonates (up to 28 days post birth) of uncertain viability or nonviable neonates will be included only to the extent of recording their birth outcome and birthweight. As the different dosing regimens follow United States guidelines and are already administered at hospitals in the US, there is no additional risk to neonates in this study.

For both pregnant women and neonates, there is a small chance of loss of confidentiality that we take every precaution to avoid.

Children, decisionally impaired adults, and prisoners will not be specifically included in this study.

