## Background

Magnesium sulfate is one of the most commonly prescribed intravenous medications in contemporary obstetric practice. Magnesium is the drug of choice for preventing seizures in women with preeclampsia, a leading cause of maternal morbidity and mortality. More than 77% of expectant mothers experience side effects related to antenatal magnesium administration. Magnesium may also negatively impact obstetric outcomes and lead to adverse neonatal effects. Current intravenous magnesium treatment for various indications (preeclampsia, tocolysis, neuroprotection) follows standardized protocols (4-6 g loading dose followed by an infusion at 1-2 g/h) based on institution preference. These protocols proposed by Prichard in 1979 were derived clinically to provide estimated serum magnesium levels necessary to treat eclamptic seizures. These standardized protocols are administered unaltered to all patients, without adjustment for maternal or fetal factors that may affect serum magnesium levels. The PI has previously constructed a detailed, robust pharmacokinetic (PK) model of intravenous magnesium sulfate administered antenatally to expectant mothers and exposed fetuses with the aim of optimizing maternal and fetal outcomes while preventing maternal and neonatal overdosing and morbidity associated with current magnesium treatment protocols.

The PK data derived from this pilot study at another academic institution suggests obese pregnant women may require an increased dose of magnesium sulfate to maintain a therapeutic serum level for prevention of eclamptic seizures ( $\geq 4.8$  mg/dL). In that pilot study, statistical modeling suggested more obese preeclamptic women take approximately twice as long as non-obese preeclamptic women to achieve steady state levels of the drug.

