## **Study Design**

The proposed study would use 1:1 allocation to randomize women with a  $\text{BMI} \geq 35 \text{ kg/m}^2$  treated with magnesium sulfate for preeclampsia to either standard dosing of the drug at OHSU (4g loading dose, followed by a 1 g/hr infusion) or to increased dosing (6g loading dose, followed by a 2 g/hr infusion). Maternal serum magnesium levels will be obtained at baseline, as well as after administration of magnesium sulfate at 1 hour, 4 hours, and at the time of delivery (within 20 minutes). We will exclude patients who are  $< 32$  weeks gestation, as these women will automatically be administered a 6g loading dose, followed by 2g/hr infusion for fetal neuroprotection. The outcome will be a comparison of the proportion of preeclamptic women in each magnesium sulfate protocol group who have therapeutic serum levels 4 hours after administration, and at the time of delivery (serum magnesium level of  $\geq 4.8$  mg/dL). We hypothesize that a significantly higher proportion of women with a  $\text{BMI} \geq 35 \text{ kg/m}^2$  will be subtherapeutic at 4 hours and at the time of delivery when administered standard dosing of magnesium sulfate. Findings from the proposed research can be used to tailor treatment for preeclampsia in obese pregnant patients.

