### e. Consent Process

Once a potential participant has been identified, the PI or appropriate research staff will approach potential participants for consent while standard laboratory workup ensues for preeclampsia. Written informed consent will be obtained after having the purpose and details of the study explained in person by the PI or other research personnel. Because study participation is limited to inpatients who are prescribed the study drug, no outside recruitment of subjects will take place.

After explaining the purpose of the study, the process of randomization, and obtaining informed consent, the PI /research personnel will use a random number generator from OpenEpi to assign the patient to one of two magnesium sulfate dosing regimens.

The PI/research personnel will review the list of daily obstetric service patients to identify possible participants for recruitment.

During the consent process, it will be emphasized to the potential research subject that the study drug is given in varying doses at different institutions and that if they choose not to participate, they will receive the dose that is standardly prescribed at OHSU for preeclampsia.

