**Information that may be abstracted from the subject's chart includes** maternal age, race, height, weight, renal function and creatinine clearance (if available), maternal heart rate variability, medical comorbidities, chorioamnionitis, labor duration, mode of delivery, gestational age, cord pH, and birthweight. These covariates may be considered in the pharmacokinetic model. These covariates demonstrate biological plausibility, and have physiologic potential to significantly impact the optimal dosing of magnesium. Additionally, maternal side effects (flushing, sedation, nausea, vomiting, respiratory rate, oxygen saturations, blood pressure, heart rate, and patella tendon reflex depression) will be assessed prospectively by a physician or research assistant at the same time-points as the PK sampling. Neonatal data will include NICU admission, need for respiratory support, need for blood pressure support, electrolyte abnormalities, feeding difficulties, intraventricular hemorrhage, necrotizing enterocolitis, seizures, sepsis, respiratory distress syndrome, retinopathy, patent ductus arteriosus, fetal/infant death.

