**4. Data Analysis**

Univariate and multivariate mixed-effects modeling will be utilized to assess the impact of various covariates on the outcome of serum magnesium level at different time points after magnesium sulfate administration. As previously described, assuming 95% of normal weight women have therapeutic serum magnesium levels after 4 hours of administration, we anticipate that 18 patients (36 total) are needed in each dosing group to detect a 50% difference in the proportion of women with a  $\text{BMI} \geq 35 \text{ kg/m}^2$  who have therapeutic magnesium levels 4 hours after magnesium sulfate administration. Based on current patient load, which includes treatment of approximately 40 preeclamptic patients per month, and the additional inclusion criteria of the disease severity requiring magnesium sulfate administration, as well as a maternal  $\text{BMI} \geq 35 \text{ kg/m}^2$ , and anticipated number of patients declining study participation, we anticipate potential enrollment of 1-2 patients per week.

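### The statement that neonates face no additional risk is unsupported, because randomisation raises magnesium exposure in one arm and no stated analysis compares the collected neonatal outcomes by arm

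*Combined protocol and SAP*

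**What the plan says.** **Risk statement.** The Vulnerable Populations section concludes that "there is no additional risk to neonates in this study". Its reason is that the regimens follow US guidelines and are already given in US hospitals. Section 8 adds that both are already used in pregnancy at the site, for different indications.

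**Background.** The same protocol says: "Magnesium may also negatively impact obstetric outcomes and lead to adverse neonatal effects". It describes the aim of the earlier pharmacokinetic work as including "preventing maternal and neonatal overdosing and morbidity associated with current magnesium treatment protocols".

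**Arms.** Study Design randomises 1:1 to "4g loading dose, followed by a 1 g/hr infusion) or to increased dosing (6g loading dose, followed by a 2 g/hr infusion".

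**Care outside the trial.** The Consent Process section tells candidates that "if they choose not to participate, they will receive the dose that is standardly prescribed at OHSU for preeclampsia".

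**Neonatal data.** Section 2 says: "Neonatal data will include NICU admission, need for respiratory support, need for blood pressure support, electrolyte abnormalities, feeding difficulties", followed by eight further items ending with death, 13 in all.

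**Analysis.** Section 4 models "the outcome of serum magnesium level at different time points after magnesium sulfate administration". Aims 1 and 1a concern the maternal serum level, and Aim 2 concerns maternal side effects.

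**Safety review.** Section 6 has the principal investigator review adverse events as they are reported, with qualifying ones going to the IRB. Section 7a lists no neonatal drug risk.

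**The concern.** Additional risk has to be measured against what the mother and baby would have received without the trial. Use of a regimen at other hospitals, or for another indication, does not answer that question. Here the alternative is the site's standard regimen, so about half of the participants get more magnesium because they enrolled. The protocol itself regards magnesium as capable of harming neonates.

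Two things are at stake. First, the ethics committee is given an unqualified statement that the protocol does not support, in a trial that section 7b says offers participants no benefit. Second, Study Design says the findings can be used to tailor treatment. A favourable maternal serum result could be used in that way without the neonatal data, already collected, being set side by side by arm.

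**Working it through.** **1. Difference in exposure.** The inputs are the two regimens in Study Design. Cumulative maternal dose at t hours, if the regimen is unchanged:

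- standard: 4 + 1 × t g
- alternate: 6 + 2 × t g

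| t | Standard | Alternate | Ratio |
|---|---|---|---|
| 4 h | 4 + 4 = 8 g | 6 + 8 = 14 g | 14/8 = 1.75 |
| 12 h | 4 + 12 = 16 g | 6 + 24 = 30 g | 30/16 = 1.88 |

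These are maternal grams and not fetal levels. The 12-hour row bears on the neonate only if delivery is that late, and time to delivery is not given.

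**2. Does the stated reason cover the enrolled women?** Study Design identifies the site's own use of the 6 g and 2 g/h regimen as fetal neuroprotection before 32 weeks. Women before 32 weeks are excluded. That precedent does not show equal neonatal risk between the arms at 32 to 42 weeks.

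**3. Where could a neonatal comparison sit?**

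| Place | Outcome addressed |
|---|---|
| Aims 1 and 1a; outcome in Study Design | Proportion with a therapeutic maternal level |
| Aim 2 | Maternal side effects |
| Hypotheses 1 to 3 | Maternal levels, maternal effects and outcomes, dosing of the mother |
| Section 4 | Serum magnesium level |
| Section 6 | Individual adverse events, not tabulated by arm |

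None compares neonatal outcomes by arm.

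**4. The plan's own sample size.** The plan gives 18 per group but states no alpha, sidedness or power. I assume two-sided 0.05 and proportions of 0.50 and 0.95. The mean proportion is 0.725.

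n = [1.96 × √(2 × 0.725 × 0.275) + z × √(0.50 × 0.50 + 0.95 × 0.05)]² / 0.45²

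- 80% power (z = 0.842): (1.238 + 0.459)² / 0.2025 = 14.2, so 15 per arm, or 19 with a continuity correction.
- 90% power (z = 1.282): (1.238 + 0.699)² / 0.2025 = 18.5, so 19 per arm.

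The stated 18 is reproduced to within a patient or so. It was set for a very large difference in a maternal laboratory result.

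**5. What 18 per arm can say about neonates.** The documents give no neonatal event rates, so the rates below are assumptions. With a common rate p in both arms, the Wald 95% half-width is 1.96 × √(2p(1 − p)/18):

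| p | Half-width |
|---|---|
| 5% | 1.96 × 0.073 = 14 points |
| 10% | 1.96 × 0.100 = 20 points |
| 20% | 1.96 × 0.133 = 26 points |
| 50% | 1.96 × 0.167 = 33 points |

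Power to detect a doubling at two-sided 0.05:

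| Rates | Normal approximation | Fisher's exact test |
|---|---|---|
| 5% v 10% | 8% | 1% |
| 10% v 20% | 13% | 6% |
| 20% v 40% | 25% | 16% |
| 30% v 60% | 44% | 36% |

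For 80% power, these doublings need 435, 199, 82 and 42 per arm.

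**6. Rare events.** With no events in either arm, the Wald interval has zero width. With 0 of 18, the exact two-sided 95% upper limit is 1 − 0.025^(1/18) = 18.5%. The Wilson upper limit is 3.84/(18 + 3.84) = 17.6%, so Newcombe's interval for the difference runs from −17.6 to +17.6 points. A small-sample method is needed.

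**The case against.** The best defence is that the protocol gives a reason for its statement. Both regimens lie within the range that the Background describes as current practice (a 4 to 6 g load, then 1 to 2 g/h), and the higher one is already used at the site. The Background's remarks on neonatal effects apply to that whole range and draw no contrast between the two regimens. This is a small pharmacokinetic study, and no neonatal comparison in 36 women could be decisive. Consent pages are not among the documents, so what participants are told about neonates cannot be judged.

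Much of this stands, and it rules out several stronger readings:

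- **That the Background flatly contradicts the risk statement.** It says only that magnesium may have adverse neonatal effects. It gives no neonatal dose-response and no difference between the regimens. The statement is unsupported rather than disproved.
- **That neonatal harm would go unexamined.** Section 2 collects the data and section 6 provides review of individual events. What is missing is a comparison between arms.
- **That the higher arm is shown to harm neonates.** Nothing in the documents shows this. The dose ratios describe maternal dose, part of the infusion is given after delivery, and section 2 allows dose reduction for symptoms, which would narrow the gap.
- **That a new aim or a powered neonatal test is required.** A descriptive table is enough, and a powered test is out of reach at this size.

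The defence does not rescue the sentence itself. Use elsewhere does not alter the fact that enrolment raises exposure for one arm. Low power also cuts both ways: a sample too small to show harm cannot support a claim of no added risk.

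**Conclusion.** The point holds in limited form. The sentence on neonatal risk is unsupported relative to the care these women would otherwise receive, and the neonatal outcomes are not compared by arm in any stated analysis.

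The size of the exposure difference, 14 g against 8 g at 4 hours, follows from the protocol's own regimens and assumes no dose change in that time. The precision figures (half-widths of 14 to 33 points) rest on 18 neonates per arm with complete data and on assumed event rates of 5% to 50%. They show that a by-arm table serves estimation only. The change is worth making because it bears on patient safety and uses data already to be collected. No view is taken on which regimen is right.

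**What to change.** 1. Reconcile the Vulnerable Populations section with the Background and the Consent Process section, by removing or qualifying the sentence on additional neonatal risk.
2. State in section 7a that magnesium may have adverse neonatal effects and that exposure differs by arm. The Background names no specific neonatal effects, so general wording is all that the document itself supports.
3. Add to section 4 one descriptive table of the section 2 neonatal outcomes by randomised arm. Give counts, risk differences and 95% confidence intervals by a small-sample method such as Newcombe or exact.
4. State the denominator for each outcome. The Vulnerable Populations section limits data on nonviable neonates and those of uncertain viability to birth outcome and birthweight, so say how these infants enter each row.
5. Say beside the table that absence of a difference is not evidence of safety.

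The cost is a less favourable risk statement, an IRB wording update and one extra table. No new data, visits, participants or dosing changes are needed.

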**c. Setting**

- The research will take place at the OHSU Labor and Delivery Unit and Antepartum Unit and the study procedures will be carried out by OHSU personnel.

**d. Recruitment Methods**

When pregnant women with preeclampsia are identified at presentation to OHSU hospital through review of the medical record, the PI and research staff will screen for participation based on maternal age, gestational age, and whether or not magnesium sulfate will be prescribed as part of usual care.

Assistance with the initial screening process will take place through resident education sessions, as well as posting of study inclusion/exclusion criteria in the resident workroom as a reminder. A study factsheet and recruitment flyer will be posted on Labor and Delivery, Antepartum, and in the resident workroom to facilitate enrollment. Recruitment outside of these areas is not anticipated due to the specific circumstances in which a potential research subject would qualify for enrollment (i.e. inpatient). Additionally, a recruitment Grand Rounds will be presented to the Department of OB/GYN to educate them regarding the study enrollment criteria.

There will be no payment for participation in the study, however, laboratory studies requested for subjects that would not have normally been requested as part of usual care (i.e. blood, urine, and cerebrospinal fluid magnesium levels), will not be charged to the subject.

### e. Consent Process

Once a potential participant has been identified, the PI or appropriate research staff will approach potential participants for consent while standard laboratory workup ensues for preeclampsia. Written informed consent will be obtained after having the purpose and details of the study explained in person by the PI or other research personnel. Because study participation is limited to inpatients who are prescribed the study drug, no outside recruitment of subjects will take place.

After explaining the purpose of the study, the process of randomization, and obtaining informed consent, the PI /research personnel will use a random number generator from OpenEpi to assign the patient to one of two magnesium sulfate dosing regimens.

The PI/research personnel will review the list of daily obstetric service patients to identify possible participants for recruitment.

During the consent process, it will be emphasized to the potential research subject that the study drug is given in varying doses at different institutions and that if they choose not to participate, they will receive the dose that is standardly prescribed at OHSU for preeclampsia.

#### **Non-English Speaking Subjects**

- Subjects who do not identify themselves as English speaking are eligible for consent if they identify as Spanish speaking and an interpreter is available to assist with the consent process and ongoing study requirements in a timely fashion. The primary study coordinator is Spanish speaking and will most often consent non-English speaking subjects. The English Consent and Authorization form will be translated into Spanish and submitted for IRB approval prior to use. Only English and Spanish speaking patients will be eligible to participate. The initiation of magnesium sulfate for preeclampsia will not be delayed to wait for the primary study coordinator or an in-person interpreter, and if the drug is ready to be administered prior to obtaining consent, the potential subject will no longer be eligible.

## **2. Procedures Involved**

After obtaining informed consent, the subject will be randomly assigned to one of two treatment groups: 1.) a starting dose of magnesium sulfate of 4g, followed by 1g every hour until 24 hours after delivery (the current standard regimen used at OHSU), or 2.) a starting dose of magnesium sulfate of 6g, followed by 2g every hour until 24 hours after delivery. There will not be a placebo arm of the study; only a smaller dose or larger dose of magnesium sulfate administered. Although the study dosing is randomized, it is not blinded and both the investigator and the research subject may know what dose of magnesium sulfate is being administered. If the subject is found to be symptomatic at any point in the study, the usual clinical care will be provided, which would include checking a serum magnesium level and decreasing the dose of magnesium sulfate, if needed. Study participation will continue; however, the timing and details of the dosing change will be recorded and used for research purposes.

If there is an indwelling intravenous catheter in place for surgery, we will attempt to use it to draw blood. We will draw a sample from a vein if we are not able to collect the samples from an existing intravenous catheter.

Specimens will be collected as follows:

- Serum magnesium before the administration of magnesium sulfate
- Serum magnesium at 1 hour, 4 hours, and delivery after the initial dose of magnesium sulfate
- Each sample will be 5-10 ml (approximately 1-2 teaspoon). The total drawn for all samples will likely not exceed 5 teaspoons.
- Urine samples will be obtained if possible at these same time points.
- If the patient requires spinal anesthesia for cesarean delivery, 0.5 ml (a few drops) of spinal fluid will be taken to check for magnesium levels at the same time the spinal anesthetic is being performed.

	Visit 1 Day 1	Visit 2 Day 1	Visit 3 Day 1	Visit 4 Day 1
Consent Discussion, Screening tests and medical history	X			
Blood draw (1 teaspoon)	X	X	X	X
Urine sample (2 teaspoons)	X	X	X	X
Time (after magnesium sulfate administration)	baseline	1 hour	4 hours	Time of delivery (within 20 mins)

**Information that may be abstracted from the subject's chart includes** maternal age, race, height, weight, renal function and creatinine clearance (if available), maternal heart rate variability, medical comorbidities, chorioamnionitis, labor duration, mode of delivery, gestational age, cord pH, and birthweight. These covariates may be considered in the pharmacokinetic model. These covariates demonstrate biological plausibility, and have physiologic potential to significantly impact the optimal dosing of magnesium. Additionally, maternal side effects (flushing, sedation, nausea, vomiting, respiratory rate, oxygen saturations, blood pressure, heart rate, and patella tendon reflex depression) will be assessed prospectively by a physician or research assistant at the same time-points as the PK sampling. Neonatal data will include NICU admission, need for respiratory support, need for blood pressure support, electrolyte abnormalities, feeding difficulties, intraventricular hemorrhage, necrotizing enterocolitis, seizures, sepsis, respiratory distress syndrome, retinopathy, patent ductus arteriosus, fetal/infant death.

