#### **Specific Aim 2: To determine if, and which, maternal side effects are more common at 1 hour, 4 hours, and time of delivery with an alternate magnesium sulfate dosing protocol in obese women.**

## Hypotheses

We hypothesize that a randomized trial of alternate dosing of intravenous magnesium in obese women will allow us to:

1. Determine optimal antenatal magnesium dosing protocols to optimize therapeutic serum magnesium levels in obese preeclamptic women.
2. Determine significant covariates and correlations between maternal serum magnesium levels and maternal side effects and outcomes.
3. Determine the optimal antenatal magnesium dose to minimize adverse drug effects while maintaining a therapeutic serum magnesium level in the mother.

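### Side effects at delivery, especially the knee reflex, are assessed when some women will have a spinal block, with no record of block status and no rule for handling it

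*Combined protocol and SAP*

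**What the plan says.** Specific Aim 2 asks if, and which, "maternal side effects are more common at 1 hour, 4 hours, and time of delivery with an alternate magnesium sulfate dosing protocol". Delivery is thus one of three named comparison times.

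Section 2 (Procedures Involved) names the signs: "maternal side effects (flushing, sedation, nausea, vomiting, respiratory rate, oxygen saturations, blood pressure, heart rate, and patella tendon reflex depression". The list ends, and the timing is set, with "patella tendon reflex depression) will be assessed prospectively by a physician or research assistant at the same time-points as the PK sampling". The visit table in that section gives the last sampling time as "Time of delivery (within 20 mins" and does not say whether this means before or after the birth.

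The same section foresees regional anesthesia at that time: "If the patient requires spinal anesthesia for cesarean delivery, 0.5 ml (a few drops) of spinal fluid will be taken".

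The chart data that may be abstracted include mode of delivery. Type of anesthesia, its timing, and whether a block is in place at an assessment are not listed. The abstracted covariates are offered, as an option, for the pharmacokinetic model. Section 4 (Data Analysis) describes only models with serum magnesium as the outcome. No section gives a scoring rule or an analysis for the side effects.

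**The concern.** A lumbar neuraxial block abolishes or depresses the knee reflex whatever the magnesium level, and it commonly lowers blood pressure and can cause nausea and vomiting. This is general clinical knowledge, not something the protocol states. For blocked women, the reflex item at delivery therefore cannot separate the two regimens, and the nausea, vomiting and blood pressure items do so less well.

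Dilution runs toward no difference, which is the less cautious direction when the question is whether a larger regimen causes more side effects. Hypotheses 2 and 3 also lean on these data, to relate serum levels to side effects and to look for a dose with fewer of them. If block status is not recorded at the check, a reader of the results cannot tell how much of the delivery comparison is affected.

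**Working it through.** **The plan's own figure.** No sample size or expected rate is given for Aim 2. The 18 per arm was set for the proportion with therapeutic magnesium at 4 hours. Alpha and power are not stated. Assume two-sided alpha 0.05 and use n = [z_α√(2p̄q̄) + z_β√(p₁q₁ + p₂q₂)]² / (p₁ − p₂)², with p₁ = 0.50 and p₂ = 0.95 from Number of Subjects.

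- 80% power: (1.96 × 0.631 + 0.842 × 0.545)² / 0.2025 gives 15 per arm, or 19 with continuity correction.
- 90% power: 19 per arm without correction.

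The stated 18 is within a patient of two of these variants. Nothing below depends on it except the number of women available.

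**Dilution.** Let f be the share of women in each arm with a block at the delivery check, and p the true rate of reflex depression from magnesium. If every blocked woman shows no reflex:

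- observed rate = f + (1 − f)p
- observed difference = (1 − f)(p_larger − p_standard)

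The documents give neither f nor p, so all values here are assumptions. Power is exact Fisher power at 18 per arm, two-sided 0.05, from binomial probabilities summed over all tables that reach P ≤ 0.05.

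| True rates | f | Observed rates | Difference | Power |
|---|---|---|---|---|
| 5% v 25% | 0 | 5% v 25% | 20 points | 25% |
| | 0.10 | 14.5% v 32.5% | 18 | 15% |
| | 0.30 | 33.5% v 47.5% | 14 | 9% |
| | 0.60 | 62% v 70% | 8 | 4% |
| | 0.90 | 90.5% v 92.5% | 2 | 1% |
| 10% v 50% | 0 | 10% v 50% | 40 | 67% |
| | 0.25 | 32.5% v 62.5% | 30 | 36% |
| | 0.50 | 55% v 75% | 20 | 16% |
| | 0.75 | 77.5% v 87.5% | 10 | 6% |

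**Chance imbalance.** With the same f in both arms, the difference in blocked share has standard deviation √(2f(1 − f)/18). This is 0.10 at f = 0.10 (1.8 women), 0.153 at f = 0.30 (2.75 women) and 0.167 at f = 0.50 (3 women). An imbalance of 3 women in 18 moves the item by (3/18)(1 − p), so by at most 16.7 points, and by 15.0 points at p = 10%. This is extra noise. It does not inflate the error rate of a randomization-valid test, and the power figures above already include it.

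**If dose affected block use.** Suppose, for illustration, 40% v 60% blocked with p = 10% in both arms. The item then differs by (0.60 − 0.40)(1 − 0.10) = 18 points with no magnesium effect on reflexes. Background says that magnesium may worsen obstetric outcomes, so this route cannot be dismissed. The documents do not show that it operates.

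**The case against.** Several points on the other side stand.

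- **The blocked share may be small.** Section 3a (Handling of Data and Specimens) expects cerebrospinal fluid specimens only rarely, while section 2 takes one whenever a spinal is needed for cesarean. Together these suggest few such spinals. They say nothing about labor epidurals, but the protocol never mentions epidurals, so any wider neuraxial use is an inference. A reader might infer that the reflex item is swamped by block in both arms. The documents do not support that.
- **No misattribution is written down.** A reader might infer that a blocked woman with an absent knee reflex is counted as a case of magnesium toxicity. The plan says only that signs are assessed. What is missing is a rule. The full-misclassification model above is the limiting case.
- **Some information exists.** Mode of delivery is listed, the abstraction list need not be exhaustive, and a spinal fluid sample would mark a spinal. But mode of delivery cannot separate spinal from general anesthesia, or vaginal birth with and without an epidural, and none of these sources gives block status at the time of the check.
- **Block is not the main limit on power.** With 5% v 25% and no block at all, power is already only 25%.
- **Sedation is a weak example.** It would come from adjunct drugs more than from a lumbar block, so it is left out of the point.

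None of this supplies a rule for the signs assessed under a block.

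**Conclusion.** The point holds as a gap in measurement at one of Aim 2's three time points. In blocked women the knee reflex carries little information on magnesium, and nausea, vomiting and blood pressure may be partly anesthetic. The plan neither records block status nor says how to treat these signs. The expected effect on the reflex item is dilution by (1 − f), plus noise from chance imbalance between two arms of 18. With f around 10% the loss is small (20 points become 18), and with f of 60% it is large (20 become 8). The documents do not say which applies.

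A reader might go further and infer systematic bias between the arms or damage to the main result. Neither follows. Randomization balances block use in expectation, and the 4-hour serum magnesium outcome does not depend on these signs. The 1-hour and 4-hour checks are affected only if a block is already in place. The conclusion rests on the clinical assumption that a lumbar block removes the knee reflex and on the protocol's own expectation of some spinals. It calls for a cheap improvement, not a redesign.

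**What to change.** In section 2, where the side-effect assessment is described:

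1. At each check, record whether a neuraxial block or general anesthesia is in place.
2. When a block is present, test an upper-limb reflex in place of the knee reflex for the research score, so that all randomized women stay in the comparison.
3. Report the delivery comparison in all women. Add a breakdown by block status as a sensitivity analysis only, and state that block status arises after randomization and may be affected by dose. Dropping blocked women from the main comparison would trade dilution for possible selection bias.

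The cost is one tick-box and a second reflex site on the form. The reflex item at delivery will mix two sites, which should be stated in the report. The change restores information on reflexes only. Nausea, vomiting and blood pressure under a block stay hard to attribute, and the breakdown can only show how far that matters. Dosing and clinical monitoring are not touched.
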